9.2 Evaluations

9.2.1 Every Follow-up Visit

- All patients will enter a common follow-up program following completion of radiotherapy. Routine follow-up care: complete head and neck examination, including mirror and/or endoscopic examination (flexible fibroscope if deemed clinically necessary by the treating physician),
- Performance Status, Weight, and Toxicity Notation
- Follow up speech-language pathology evaluation will include clinical swallow assessment and inter incisors distance measurement. Prophylactic exercises will be reviewed as well as the importance of oral hygiene and strategies to ameliorate xerostomia. Patients' ability to follow through with recommended exercises and strategies will be recorded. Documentation of the presence of a gastrostomy feeding tube, estimated percent of oral alimentation/hydration via the feeding tube; estimated percentage of PO intake at baseline. In addition, at the first post-treatment follow up examination (6-8 wks), a MBSS will be obtained, even in absence of specific symptoms as well as a Montreal Cognitive Assessment (MCA).

9.2.2 Studies

- Biopsy: Any suspicious mucosal lesion in the upper aerodigestive tract; pharyngeal pain referred to the ear should trigger a search for recurrent disease; any firm node that persists longer than four weeks; epistaxis; chronic nasal congestion though not to be due to radiation mucosal changes.
- PET/CT as per 9.1
- Modified barium swallow test will be obtained 6-8 weeks after completion of treatment. Subsequently, a MBSS will be obtained only if clinically indicated.
- Audiogram: Pre-RT if the inner ear receives a mean dose ≥ 40 Gy, or if any hearing loss, vertigo or tinnitus occur. Subsequent audiograms will be conducted at the discretion of treating physician as indicated by patient reported symptoms

9.3 Response Criteria

9.3.1 Tumor Response Measurements (RECIST Criteria)

The use of the flexible fibroscope may be used for tumor measurement. This will be determined by the treating physician.

All tumor measurements must be recorded in centimeters and should consist of the longest perpendicular diameters. In no case will complete response be reported unless all clinically demonstrable disease has disappeared.

9.3.1.1 Complete Response (CR)

No measurable tumor is present on clinical and radiological examination.

9.3.1.2 Partial Response (PR)

A greater than 50% decrease in the product of the longest diameter multiplied by its perpendicular diameter when compared to the initial 'on-study product, providing there is no increase greater than 25% of any area of known disease or the appearance of any new lesions.

9.3.1.3 Minor Response (MR)

The difference between products is less than 50 percent of the initial product. No new lesions have appeared.

9.3.1.4 Stable Disease (SD)

Tumor size has not changed; no progression, no new lesions.

9.3.1.5 Progression (PD)

The second product shows a greater than 25 percent increase over the initial product, or appearance of new lesions.

9.4 Definition of locoregional control

9.4.1 A patient is defined as locoregionally controlled if he achieves a CR at both the primary site and the neck within 10-12 weeks from treatment end as previously defined (7.2, 9.3.1.1).

9.4.2 Patients who shows a CR at the primary site and a <CR (residual disease) in the neck at re-evaluation imaging 8-10 weeks, are evaluated for neck surgery (7.2). Patients who are cleared for residual disease in the neck by surgery are still considered having achieved a CR after treatment provided there is no residual disease left after surgery

9.4.3 Patients who fail to achieve a CR with or without neck surgery are scored as failures at day 1 of radiotherapy.

9.4.4 In order to remain controlled, patients who achieve a CR with or without neck surgery must remain cancer free at both T and N during each subsequent follow up examination (9.2.1). Treatment failure is defined as the documented (biopsy-proven) reappearance of disease at the primary site and/or the neck.

9.4.5 Distant disease is defined as the clinical or radiological appearance of metastases below the clavicles.

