7 SURGERY

7.1 Upfront neck surgery (*excisional biopsy or neck dissection*) is at the discretion of the surgeon.

7.2 Surgery at the primary tumor is expected to consist of an incisional biopsy for diagnostic purposes only. An excisional surgery (i.e. tonsillectomy) is allowed if other gross disease is present e.g. neck lymph nodes. Patient will be also staged according to the clinical stage before any surgical procedure.

7.3 Surgery should be performed for persistent tumor following RT as documented by PET/CT (CT with thin slices and i.v. contrast for the HN part) at 8-12 weeks after the end of the treatment, or at the discretion of the surgeon. Suspected residual disease is defined as persistent FDG uptake at the site of the primary tumor qualitatively assessed by comparing to background and corresponding abnormal tissue on CT. Surgery is recommended for PET/CT positive residual disease, as described. A selective neck dissection is appropriate for patients with positive residual disease in levels II-IV and levels IB and V were initially negative. A comprehensive neck dissection is recommended in the other cases.

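### Locoregional control rests on two response criteria that do not match, so a measurable but FDG-negative neck node can be scored in opposite ways

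*Combined protocol and SAP*

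**What the plan says.** Locoregional control is one of the two primary endpoints (sections 2.1 and 10.3.1), with a goal of 85%. Its scoring draws on three places.

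- **Section 9.3.1.1** defines CR: "No measurable tumor is present on clinical and radiological examination". Section 9.3.1 adds: "In no case will complete response be reported unless all clinically demonstrable disease has disappeared". Partial and minor response (9.3.1.2, 9.3.1.3) are graded by the product of diameters. FDG uptake appears in none of these definitions.
- **Section 7.3** uses the PET/CT result and asks for a matching CT abnormality as well as FDG uptake: "Suspected residual disease is defined as persistent FDG uptake at the site of the primary tumor qualitatively assessed by comparing to background and corresponding abnormal" (the sentence closes by naming the CT finding). It then says: "Surgery is recommended for PET/CT positive residual disease, as described". The scan is placed "at 8-12 weeks after the end of the treatment, or at the discretion of the surgeon". For the neck it speaks only of positive disease by level: "A selective neck dissection is appropriate for patients with positive residual disease in levels II-IV".
- **Section 9.4** combines the two. 9.4.1 requires a CR at primary and neck and cites 7.2 and 9.3.1.1 for the definition. 9.4.2 treats less than CR in the neck as residual disease and sends the patient for surgical evaluation. It adds: "Patients who are cleared for residual disease in the neck by surgery are still considered having achieved a CR after treatment", on condition that nothing is left after surgery. 9.4.3 covers the rest: "Patients who fail to achieve a CR with or without neck surgery are scored as failures at day 1 of radiotherapy". Later failure under 9.4.4 needs biopsy proof; a day-1 failure under 9.4.3 does not.

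Section 7.2 covers surgery at the primary and staging and defines no response. The reference to it in 9.4.1 and 9.4.2 appears to mean 7.3.

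**The concern.** If 7.2 is a slip for 7.3, then 9.4.1 invokes a size-based and a PET/CT-based criterion together, and they can disagree. The case that exposes this is a neck node that has shrunk, is still judged measurable and takes up no FDG. No sentence says how to score it when it is observed.

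A rule for a primary endpoint should give the same score whoever applies it. Here the score can depend on the assessor's reading and on whether the neck was operated on, as well as on what the tumor did. The trial is single-arm, so no control group would share the misclassification. If the question is left open, it will be settled patient by patient after outcomes are known. Day-1 failures also enter the failure counts in the stopping table of section 10.1.

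**Working it through.** **1. One patient under each rule.** Primary in CR; one neck node still judged measurable; no FDG uptake.

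| Section | Question | Literal result |
|---|---|---|
| 7.3 | PET/CT-positive residual disease? | No |
| 9.3.1.1 | CR? | No, if the node counts as measurable tumor |
| 9.4.3 | Score if observed | Failure at day 1, even with no later recurrence |
| 9.4.2 | Score if dissected with no disease left | Controlled |

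**2. The plan's own figures (section 10.1).** All reproduce.

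- Evaluable patients: 60 × (1 − 0.15) = 51, which the plan gives as 50.
- Exact 95% intervals at n=50: 42/50 gives 70.9–92.8% (plan 71–93); 45/50 gives 78.2–96.7% (plan 78–97); 47/50 gives 83.5–98.7% (plan 83–99).
- One-sided 90% lower bounds for 5/10, 9/20, 12/30 and 15/40: 26.7%, 29.3%, 27.7%, 27.1%, as in the stopping table.

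**3. Effect per patient.** 1/50 = 2 points. The goal lies between 43/50 = 86% and 42/50 = 84%. Starting from 45/50 = 90%, three reclassified patients give 42/50 = 84%.

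**4. Effect by frequency.** Let q be the share of otherwise-controlled patients who have such a node and are observed. The documents give no q, so a range is shown. True control of 90% is also an assumption.

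- Scored control = 0.90 × (1 − q).
- Because 0.85 × 50 = 42.5, an estimate of at least 85% needs X ≥ 43, with X binomial (50, scored control).
- Stopping is the exact binomial probability of reaching 5/10, 9/20, 12/30 or 15/40 failures at any of the four looks, with every failure taken as known at its look.

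| q | Scored control | P(estimate ≥ 85%) | P(crossing failure table) |
|---|---|---|---|
| 0 | 90.0% | 88% | 0.2% |
| 1% | 89.1% | 83% | 0.2% |
| 2% | 88.2% | 77% | 0.4% |
| 5% | 85.5% | 56% | 0.9% |
| 10% | 81.0% | 24% | 3% |
| 20% | 72.0% | 2% | 23% |

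For each frequency this is the upper case, because it assumes that every such patient is observed and scored literally.

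**The case against.** The strongest reply is that the sections can be read together. 9.4.1 cites two sections for CR. 9.4.2 glosses less than CR as residual disease, the term 7.3 defines by PET/CT. Note 5 to Table 9 makes PET/CT the test of response. 9.3.1.1 speaks of measurable tumor, not a measurable node. On this reading an FDG-negative remnant is not residual disease, so it is neither less than CR nor a day-1 failure. This stands as a possible reading. It is not written down, and the literal reading is equally open, so the reply reduces the defect to an ambiguity without removing it.

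Three stronger conclusions that a reader might draw are not supported:

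- **That a node above 1 cm is by rule a partial response.** The 1 cm figure is in 5.3.2, under target definition for radiotherapy contouring. Section 9.3 sets no nodal size for measurable disease, so the problem is confined to nodes an assessor still calls measurable.
- **That 7.3 explicitly clears an FDG-negative node.** Its FDG wording names only the primary site; extending it to the neck is inference. If it does not extend, the size rule governs the neck alone and the observed patient is still a day-1 failure.
- **That such patients will be common, or that a working treatment would be halted.** Eligibility up to N3 makes the case foreseeable, but no frequency is given. At 1–2% the stopping probability stays at or below 0.4%, and crossing only pauses the trial for committee review. Section 10.3.1 reports a rate with an exact interval and no pass/fail test.

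Two further points are fair. Surgery for residual disease is part of the planned treatment, so crediting surgical clearance is deliberate. And in a de-escalation trial, counting doubtful residua as failures is a defensible conservative choice. The plan does not say that it makes that choice.

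**Conclusion.** The concern holds as an unresolved mismatch of definitions in a primary endpoint. It does not depend on any rate: 9.3.1.1 and 7.3 use different criteria, 9.4.1 and 9.4.2 cite a section that defines no response, and no sentence scores the observed, measurable, FDG-negative node. The same patient can therefore be scored as a day-1 failure or as controlled.

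The size is conditional. It is 2 points of control per patient at n=50. Under 90% true control with all such patients observed, the chance of reaching an 85% estimate falls from 88% to between 83% (q = 1%) and 2% (q = 20%). The effect on the stopping table is small unless such patients are frequent. The main harm is to the endpoint estimate. The plan's own intervals and stopping bounds are correct. Severity: should fix.

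**What to change.** Reconcile 7.3, 9.3.1.1 and 9.4.1–9.4.3 so that one stated response criterion scores the endpoint at both primary and neck, and correct the reference to 7.2. For endpoint scoring only:

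1. State that an anatomic residuum not meeting the PET/CT criterion for residual disease is not a day-1 failure. It is followed under 9.4.4 and becomes a failure on later documented disease.
2. State how patients are scored when CT or MRI replaces PET/CT. Note 5 to Table 9 arguably allows this for the response scan, and an FDG-based rule would then have no input.
3. Report a sensitivity analysis that counts all such residua as failures.

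No surgical rule is proposed or needs to change.

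The cost is amendment wording and one extra tabulation; where PET/CT was done, the data already exist. The price is a somewhat more lenient primary scoring. A residuum that harbours tumor would count only when later documented. That is not assured within two years, because 9.4.4 requires biopsy proof and about 15% of patients are expected to die before then. The sensitivity analysis bounds this effect.

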9.5 Scoring of toxicity (see also 5.11)

9.5.1 'Severe' toxicity is considered the one grade 3 or more in the CTCAE 4.0 (Appendix 1). Therefore, event is considered the presence of grade 3+ toxicity.

9.5.2 Similarly, in a 0-10 scale, 7 or more is considered `severe` (Appendix 2 and 3) ⁴⁸.

9.6 Criteria for Removal from Treatment

9.6.1 Progression of disease while on treatment.

9.6.2 Sustained severe radiation mucositis resulting in dehydration and poor nutrition unresponsive to tube feeding and break from radiation for up to 2 weeks. Every effort should be made to sustain the patient so as to avoid such complications. Should the patient be removed from study, surgical removal followed by radiation post-operatively may be attempted.

9.6.3 Patients' wishes to stop participation on the trial.

10 STATISTICAL CONSIDERATIONS

10.1 Sample Size

The accrual rate for this study is expected to be approximately 10 patients per year, over a 6-year accrual period. This would yield an expected sample size of 60 patients. The primary objective of this study is to estimate the prevalence of toxicity and efficacy two years following treatment administration. We expect approximately 15% of patients to die before reaching two years post-treatment, so our sample size for evaluation of our primary objective has been adjusted to 50 patients. The goal of this study is to demonstrate a maximum grade 3+ toxicity rate of 15% between six months and two years after treatment administration and a minimum locoregional tumor control rate (efficacy) of 85%. The table below shows the precision we have to estimate these endpoints with a sample size of 50 patients.

Endpoint	Prevalence	Exact 95% Confidence Interval	Precision (Half the width of the confidence interval)
Toxicity	2%	0.05 – 11%	5.5%
	6%	1 – 17%	8%
	10%	3 – 22%	9.5%
	14%	6 – 27%	10.5%
Efficacy	84%	71 – 93%	11%
	90%	78 – 97%	9.5%
	94%	83 – 99%	8%

The locoregional tumor control rate in this patient population is expected to be at least 85%. We will ensure that this treatment does not reduce toxicity at the expense of efficacy. At the same time, we will monitor for excess toxicity. If convincing evidence develops that:

- Locoregional control failure rate exceeds 25%; or
- Prevalence of new grade 3+ toxicities six months post-treatment exceeds 25%, the study will stop pending a data safety monitoring committee review. The complete stopping

guideline scenarios are shown in the table below, with the proportion of toxicities and failures being considered for the first 10, 20, 30 and 40 patients enrolled. For example, if 9 of the first 20 patients have a grade 3+ toxicity six months after treatment, the study will stop. If 9 patients have either a grade 3+ toxicity or fail, e.g., 4 have toxicity and 5 fail, the trial will not stop. Once the 40th patient reaches six months of follow-up, we expect to have enrolled 48 out of the total 60 patients on the study. At this point, monitoring for excess toxicity or failures will stop, as the trial's accrual phase will nearly be completed. The upper bound for the confidence intervals is 100%.

Toxicity [Locoregional Control Failure Rate]	Number of patients who develop a toxicity [fail]	Number of patients enrolled	Lower bound of exact one-sided 90% confidence interval
25%	5	10	26.7%
	9	20	29.3%
	12	30	27.7%
	15	40	27.1%

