1.4 Treatment morbidity

While contemporary results for ORO-SCC are improved compared to historical controls⁷, treatment morbidity on selected organs/tissues may have increased as well, bringing into question the real advantage in terms of therapeutic index.

Attention has been focused on organs and structures involved in swallowing that are in close proximity to ORO-SCC²⁷. Several papers have reported deterioration of swallowing function after RT+CHT (summarized by²⁸). In one study, the incidence of severe aspiration was 11% (7/63 pts) before radiotherapy and 38% (24/63 pts) afterwards, with 6 pts dying from complications of aspiration²⁹. In another report on 96 pts after radiotherapy, 31 (32%) had clinically significant aspiration and 36 (37%) developed a stricture³⁰. Altogether the results show that a more aggressive approach may yield better oncologic outcome but at a greater expense in terms of both sub-acute and late toxicity. Currently up to 15% of patients are long-term PEG tube dependent after combined chemotherapy and IMRT for advanced oropharyngeal cancer³¹. In another study of sequential therapy (induction chemotherapy followed by chemoradiation), Goguen et al periodically assessed the swallowing status of 54 head and neck cancer patients³⁰.

At one year follow up, 80% were able to eat either a regular or a soft diet and 19% still had their gastrostomy feeding tube.

In addition to the salivary glands and those structures involved in swallowing function (including the larynx), several other structures can potentially be affected: mandible-osteonecrosis, brachial plexus-palsy, thyroid gland-hypothyroidism, masticator muscles and temporomandibular joints – trismus, oral mucosa-mucositis, ears-deafness, sternocleidomastoid muscles-fibrosis, carotid arteries-stroke.

Late toxicity after (chemo)radiotherapy for head and neck SCC is, in general, poorly documented, but unfortunately quite prevalent. A retrospective analysis of patients treated with concomitant radiotherapy (3D conformal) and chemotherapy for advanced head and neck cancer within 3 RTOG studies (RTOG 91-11, 97-03, and 99-14) showed that 43% of assessable patients had a severe late toxicity defined as chronic grade 3 to 4 pharyngeal/laryngeal toxicity and/or requirement for a feeding tube ≥ 2 years after registration and/or potential treatment-related death (eg, pneumonia) within 3 years³².

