5.12 Toxicity Reporting Guidelines

5.12.1 For both acute and late effect, the NCI CTCAE Version 4.0 will be used (Appendix 1). All events will be recorded and loaded into software that is routinely used for clinical purposes in our Department called Mosaiq (v1.6 IMPAC, Sunnyvale, California).

5.12.2 The Head and Neck Cancer specific module of the MD Anderson Symptom Index (MDASI-HN)(Appendix 2) and the Xerostomia questionnaire (Appendix 3) will be used as patient-reported outcome instruments^{48,49}

5.12.3 The swallowing related instruments (see 1.6) are: Penetration/Aspiration scale (Appendix 4); Montreal Cognitive Assessment (Appendix 5); MD Anderson Dysphagia Inventory (MDADI)(Appendix 6).

5.12.4 All life-threatening (*grade 4*) toxicities from protocol treatment will be reported to the PI within 24 hours of discovery. **Institutional guidelines will be followed in reporting serious adverse events to the IRB.**

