10.3 Analysis of Endpoints

10.3.1. To achieve a prevalence of grade 3+ toxicities between six months and two years post-treatment <15% while maintaining a locoregional tumor control of at least 85% during the same time interval.

The primary endpoints, prevalence of toxicity and locoregional control rate, will be reported for all patients with an exact 95% confidence interval.

10.3.2. To determine the nature and prevalence of side effects at different time intervals and describe their relationship to pre-treatment function (toxicity) and local dose and treated volume.

Patients will be grouped by whether they had none or a grade 0-2 toxicity versus a grade 3+ toxicity. We will tabulate the frequency of patients in each group by a dichotomous measure of dose and tests for differences with a Chi-square or Fisher's exact test. Patients will also be grouped dichotomously by the number of side effects experienced

and frequencies will be compared to dose category and toxicity category using Chi-square or Fisher's exact tests.

10.3.3. To determine the quality of life of surviving patients.

The results of the Head and Neck MD Anderson Symptom Inventory (MDASI-HN) will be calculated for each patient. The mean score will be reported with a 95% confidence interval. The range and quartiles of the distribution of scores will also be reported.

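### A treatment-related death before month six falls outside the primary toxicity window and may not reach the toxicity stopping count

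*Combined protocol and SAP*

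**What the plan says.** **Event by grade.** Section 9.5.1 sets the threshold at CTCAE grade 3 or more and concludes: "Therefore, event is considered the presence of grade 3+ toxicity". Appendix 1 has a grade 5 column, which is death for most items. Nothing in 9.5 says when a death must occur to be counted.

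**Stopping rule.** Section 10.1 stops the study, pending committee review, if there is convincing evidence of "Prevalence of new grade 3+ toxicities six months post-treatment exceeds 25" (per cent). Its worked example counts patients who have the toxicity six months after treatment. The table beneath heads its count column with patients developing a toxicity, and its denominators are patients enrolled. Toxicities and locoregional failures are counted separately.

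**Primary endpoint.** Section 10.3.1 aims for a "prevalence of grade 3+ toxicities between six months and two years post-treatment <15" (per cent) and reports it for all patients with an exact 95% interval. Section 10.1 uses the same window. Section 2.1 and the schema instead give prevalence at two years.

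**Deaths.** Section 10.1 states: "We expect approximately 15% of patients to die before reaching two years post-treatment". It then moves from 60 to 50 patients for its precision table. No section says how a death enters the toxicity count.

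**The concern.** Both toxicity counts are built around a patient's status at or after month six. That suits transient acute toxicity, which section 1.4 describes as a wave that has settled by then. A fatal toxicity does not settle. If it occurs before month six, the patient is no longer there to show a grade 3+ event in the window.

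In that case the most severe toxicity leaves no trace in the toxicity rate and might not move the toxicity boundary. Two cohorts with the same number of severe toxicities could then report different rates, with the lower rate in the cohort where more of them were fatal. Deaths of this kind are not unthinkable: section 1.4 cites a 63-patient series "with 6 pts dying from complications of aspiration". The same section cites a severe late toxicity composite that does include possible treatment-related death, so there is a precedent in the protocol itself.

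**Working it through.** **Step 1: where a treatment-related death lands**

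| Time of toxic death | Prevalence at two years (2.1, schema) | Six months to two years, all patients (10.3.1) | Stopping count (10.1) |
|---|---|---|---|
| Before month six | not counted | not counted | counted only if the trigger means by six months |
| Month six to two years | not counted | counted | depends on status at month six; a later death is not addressed |

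**Step 2: reproduce the plan's stopping bounds.** The exact one-sided 90% lower bound for x events in n patients is the 10th percentile of Beta(x, n − x + 1).

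| Boundary | Plan | Reproduced | One event fewer |
|---|---|---|---|
| 5/10 | 26.7% | 26.73% | 18.8% |
| 9/20 | 29.3% | 29.29% | 24.9% |
| 12/30 | 27.7% | 27.73% | 24.8% |
| 15/40 | 27.1% | 27.14% | 24.9% |

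All four agree, and each boundary is the smallest count whose bound exceeds 25%. The arithmetic of the rule is sound.

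**Step 3: effect at one look.** Suppose 9 of the first 20 have grade 3+ toxicity and one of the nine died of it before month six. Counted, 9/20 has bound 29.3% and the study stops. Not counted, with the patient kept among the 20 enrolled, 8/20 has bound 24.9% and it continues. (Removing the patient altogether gives 8/19 with bound 26.3%, but the table has no row for 19.)

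**Step 4: effect over the four looks.** Exact binomial recursion over boundaries 5, 9, 12 and 15 at 10, 20, 30 and 40 patients, assuming 20% non-fatal counted toxicity:

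| Additional early fatal toxicity (assumed) | Chance of stopping, deaths not counted | Deaths counted |
|---|---|---|
| 2% | 4.4% | 7.1% |
| 5% | 4.4% | 13.3% |
| 10% | 4.4% | 30.5% |
| 15% | 4.4% | 53.8% |

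The last row is an extreme: it would make all the deaths that 10.1 expects by two years both toxic and early.

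**Step 5: effect on the primary endpoint.** Enrolled 60; planned deaths 15%, so 60 × 0.15 = 9 and 60 − 9 = 51 survivors (10.1 uses 50). Assume 7 non-fatal events, all among survivors.

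- Survivors only: 7/51 = 13.7% (95% CI 5.7 to 26.3).
- All 60, toxic deaths not counted: 7/60 = 11.7%.
- All 60, 1 toxic death counted: 8/60 = 13.3%.
- All 60, 2 counted: 9/60 = 15.0%.
- All 60, 3 counted: 10/60 = 16.7% (95% CI 8.3 to 28.5).

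**Step 6: direction.** Take 9 severe toxicities in 60 patients, 15.0%. If 1, 2 or 3 of the nine are fatal and leave both numerator and denominator, the rate becomes 8/59 = 13.6%, 7/58 = 12.1% or 6/57 = 10.5%.

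**The case against.** A reader might infer that fatal toxicity is excluded from both counts. The documents do not support that. Grade 5 is an event by grade under 9.5.1, and no sentence removes deaths. The stopping table's heading, over patients enrolled, can be read as a cumulative count that keeps an early death. Reporting for all patients in 10.3.1 would count a toxic death between six months and two years.

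Three further inferences also go too far.

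- **The 50 patients in 10.1 are the analysis set, so deaths are dropped.** The 50 supports a precision table; it is not stated as an exclusion, and 10.3.1 points the other way. The 7/51 figure therefore illustrates a survivors-only reading and is not the plan's declared analysis.
- **A toxic death before the response scan becomes a locoregional failure.** Section 9.4.3 says "Patients who fail to achieve a CR with or without neck surgery are scored as failures at day 1 of radiotherapy" but does not say that death before assessment is such a failure. If it were read that way, the death would be misclassified but would still count towards the failure boundary.
- **Deaths escape reporting because 5.12.4 names only grade 4.** The rule that such "toxicities from protocol treatment will be reported to the PI within 24 hours of discovery" does omit grade 5, but the next sentence sends serious adverse events to institutional reporting.

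It can also be argued that section 2.1 concerns late toxicity, so leaving early events out is a design choice. That has force for the primary endpoint, where adding early deaths changes what is estimated; it has less force for a stopping rule meant to detect excess harm. Finally, the numerical cases are chosen, the 20-patient example sits one event from the boundary, and the intervals in step 5 overlap widely. The cited aspiration deaths come without timing and from a different series.

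What remains is the death before month six, and the conflict between the two endpoint wordings.

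**Conclusion.** The point holds as a gap in the counting windows. A treatment-related death before month six is outside the primary toxicity endpoint on every wording. It is outside the stopping count on the more natural reading of the trigger and worked example, though the table heading leaves the other reading open. Later toxic deaths count under 10.3.1 but not under 2.1.

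The size depends on a toxic-death rate that the documents do not give. With 7 non-fatal events, one counted death over all 60 patients leaves the estimate at 13.3%, under the goal. Two put it at 15.0%, which no longer meets the below-15% wording of 2.1 and 10.3.1 and sits exactly on the maximum in 10.1. Three exceed either wording. For the stopping rule, one uncounted death changes the decision only when the count is at the boundary.

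This should be fixed, with moderate confidence. The case is stronger for the stopping rule than for the late-toxicity endpoint.

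**What to change.** - **Section 10.1:** state that any death attributed to protocol treatment, from the start of treatment, counts as a grade 3+ event in the toxicity stopping table when it occurs, and that the patient stays in the denominator.
- **Section 10.3.1:** state that treatment-related deaths up to two years count as grade 3+ events and stay in a denominator of all treated patients. Also report the late-only rate, with deaths before six months shown separately, so that the late-toxicity question can still be answered.
- **Sections 2.1, 10.1, 10.3.1 and the schema:** reconcile prevalence at two years with the six-month-to-two-year window.
- **Section 5.12.4:** naming grade 5 beside grade 4 is a minor tidy-up.

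The cost is wording. The toxicity rate may look slightly less favourable, and attributing deaths to treatment needs a judgement, so the plan should say who makes it.
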